1. STUDY BACKGROUND

Despite improvement in short-term graft outcomes in organ transplant, transplant patients still have to take on complex medication regimens to achieve current results. Adherence to these complex medications is an important problem in light of the potential risk of acute and chronic rejection and the associated burden of increased hospitalization, cost, and diminished quality of life that results from missed doses and poor overall drug taking. Part of the diminished quality of life is also tied to the bothersome symptoms patient feel after transplant. Most patients experience symptoms that relate to either the overall transplant immunosuppression or medication specific side effects. In the BENEFIT and BENEFIT-EXT trials, >60% of patients reported tiredness and lack of energy as an issue¹. Sleep problems, mood swings, restlessness, anxiety, depression, and concentration and memory difficulties appeared in approximately 50-60% of patients. In addition to these symptoms, >38% patients also reported numerous others side effects that have been strongly associated with calcineurin-inhibitors such as tacrolimus that include dizziness, muscle cramps, trembling hands, tingling in hands and feet, and headache.

2. STUDY RATIONALE

We hypothesize that the use of once-daily Envarsus XR® decreases some transplant- and tacrolimus-related adverse symptoms and potentially leads to improvement in quality of life and medication adherence when compared to twice-daily tacrolimus. In order to assess this hypothesis, a prospective, multi-center, observational, open-label, pilot study to investigate medication adherence and patient reported symptom occurrence and interference with daily life comparing once-daily Envarsus XR® and twice-daily immediate release tacrolimus in adult renal transplant recipients (SIMPLE) is being proposed.

The primary objective of this study is to compare tacrolimus formulations (Envarsus XR® versus twice a day tacrolimus) with the hypothesis that Envarsus XR® improves transplant- and tacrolimus- associated symptoms when compared to a twice a day tacrolimus regimen. In addition, as part of this study, adherence, additional patient reported outcomes (PROs), patient satisfaction, and health related quality of life (HRQoL) will also be measured. There is currently a limited amount of data available describing the side effects/symptoms that are most important (i.e. occur most often and are poorly tolerated) to transplant patients taking tacrolimus immunosuppression. These symptoms/side effects could clearly impact medication adherence. Furthermore, no data currently exists as to how these symptoms/side effects relate to adherence, quality of life, and patient satisfaction. This study will assess the correlation between adherence, PROs, patient satisfaction, and health related quality of life (HRQoL). It is also possible that if the increase in adherence is large enough; there could be a sufficient change in long-term patient risk for antibody mediated injury and subsequent decrease in hospitalization and cost.

3. OBJECTIVE AND ENDPOINTS

Primary Objective: The primary objective of the study is to determine if treatment with Envarsus XR® reduces a group of side effects that are commonly associated with calcineurin-inhibitor therapy.

Overall Hypothesis: Treatment with Envarsus XR® leads to improved total *calcineurin inhibitor-related symptom (CIRS) score* at 1 year after kidney transplantation compared to immediate-release, twice-daily tacrolimus.

Clinical Study Protocol [#SIMPLE]

Primary Endpoint: Difference in mean calcineurin inhibitor-related symptoms severity score at 12 months post- kidney transplantation in Envarsus XR® group vs Control (immediate-release, twice-daily tacrolimus) group.

The CIRS is a questionnaire that assesses five symptoms (from PRO-CTCAE) that have been shown to be associated with calcineurin inhibitors. These symptoms include trembling hands, muscle cramps, muscle weakness, swollen gums, and increased hair growth. Each symptom is based on symptom severity in the last 7 days scaled from 0 (none) – 4 (very severe). The cumulative score ranges from 0-20. Based on internal data, we expect a mean CIRS score in the control group (immediate release tacrolimus) to be around 3.8 ± 3.6 and hypothesize a 30% reduction in the Envarsus XR® group. This reduction is equivalent to a 1 point difference on the 0-20 scale or a standardized effect size (mean difference / standard deviation) of 0.29.

Secondary Endpoints:

1. Reduction in the population mean of any one of the five individual CIRS item including: trembling hands, muscle cramps, muscle weakness, swollen gums, and increased hair growth between the two treatment groups at 12 months
2. Total percent of patients in each treatment group with a severe or very severe score (3 or 4) on any CIRS item 12 months.
3. Difference in mean transplant-related symptoms (TRS) score between treatments at 12 months post-transplant.

The TRS is a multi-item questionnaire capturing 15 symptoms (from PRO-CTCAE) that have been shown to be associated with transplant and general health-related quality of life improvement. These symptoms include change in taste, constipation, diarrhea, swelling in arms or legs, palpitations, dry skin, darkening of skin, blurry vision, headache, insomnia, anxiety, sadness, discouraged, increase in appetite, and fatigue. Each symptom is based on symptom severity in the last 7 days and scaled from 0 (none) – 4 (very severe). Some symptoms also have added questions pertaining to frequency and/or interference with daily activities. The sum of the severity score ranges from 0-60. The improvement in transplant symptoms will be measured by the difference between treatment groups in the mean TRS score.

4. Improvement in health-related quality of life (HRQoL), as measured by the PROMIS-29 health profile, will be compared between groups at 12 months post-kidney transplantation. The PROMIS-29 produces scores for depression, anxiety, fatigue, pain interference, sleep disturbance, physical function, participation in social roles, and pain intensity. Physical and mental health summary scores will also be calculated.

Standardized effect sizes (mean difference / standard deviation) for differences in HRQOL (PROMIS-29) scores will be calculated to compare twice daily immediate release tacrolimus oral to Envarsus XR®.

Clinical Study Protocol [#SIMPLE]

5. Improvement in individual symptoms captured in the TRS questionnaire will be compared.

The standardized effect size (mean difference / standard deviation) on TRS score will be calculated and compared between treatments. Individual TRS items will be classified as improved, worsened, unchanged and compared between treatments.

6. Improvement in overall tolerability or patient bother due to side effects, measured by item GP5 (“I am bothered by side effects of treatment”) from the FACT-G.

Patients’ GP5 responses will be classified as improved, worsened, or unchanged and compared between treatments.

7. Improvement in mean taking adherence, defined as the percent of prescribed doses taken each day (as measured by electronic monitoring), rates between groups.

The assumption is that the mean taking adherence will 75% for the twice-daily immediate release tacrolimus and 90% for the Envarsus XR® (and standard deviations of 38% and 30%, respectively).

8. Improved in patient medication satisfaction as assessed by Transplant Satisfaction Questionnaire for Medication (question 14) at 12 months post-transplant.

Responses to the Transplant Satisfaction Questionnaire for Medication (question 14) will be compared between twice daily immediate release tacrolimus oral and Envarsus XR®.

9. Correlation between de novo DSA (dnDSA, collected as part of standard of care in MTA-K) and degree of taking and timing adherence.

Proportion of patients at different adherence thresholds (>70% vs ≤70%, >80% vs ≤80%, >90% vs ≤90%, and 100% vs below 100%) of taking and timing adherences over 12 months post-transplant will be correlated with the presence or absence of dnDSA by 12 months post-transplant.

10. Safety and tolerability of Envarsus XR, as measured by incidence of adverse events (AEs), changes in clinical safety labs, and hospitalizations.

Difference between treatment groups in safety parameters including the incidence of adverse events (AEs), changes in clinical safety labs, and hospitalizations.

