- Adverse Events: During the entire study period, each patient will be monitored at least monthly for trough blood levels, and undergo safety and adverse event assessments as per standard of care. The patient will be followed as appropriate to maintain the tacrolimus trough drug levels of 8 to 10 ng/ml in the first month post-transplant and 6 to 8 ng/ml thereafter.
 - AEs and SAEs will be assigned based on Common Toxicity Criteria for Adverse Events (CTCAE) definitions and tabulated as incidence rates per tacrolimus formulation.
 - Regular monitoring and summaries of hematology, blood chemistries, and urine results.
 - Regular monitoring of vital signs, physical condition, and body weight measurements.
 - Clinically significant infections (confirmed by culture, biopsy, genomic, radiologic, or serologic findings) that requires hospitalization or active anti-microbial treatment will be tabulated as incidence rates per tacrolimus formulation.
 - Cytomegalovirus (CMV), BK Virus, and Epstein-Barr disease will be tabulated as incidence rates per tacrolimus formulation.
 - dnDSA and rejection events are collected as part of standard of care in MTA-K
 - Estimated glomerular filtration rate (eGFR) will be estimated using the MRDR formula.
- Patient-Reported Measures: Patients will complete surveys on their own unless they are unable to. Surveys will be administered electronically so that data will be recorded in the study's database immediately and securely. The following patient reported outcomes measures will be assessed at both study visits.
 - HRQoL: PROMIS -29 profile (29 questions) measuring depression, anxiety, fatigue, pain interference, sleep disturbance, physical function, participation in social roles, and pain intensity
 - Symptoms: Calcineurin-inhibitor related symptoms (5 items) and the Transplant related symptoms (15 items) – items from PRO-CTCAE or in PRO-CTCAE format.
 - Symptoms/Tolerability: FACT- G (GP5) – Single item bothersome assessment (1 question).
- Adherence/Medication Satisfaction Measures: The following adherence tools/measures will be assessed at each study visit throughout the study for those patients capable of using an adherence measurement via a digital capture system:
 - The PROMIS Self-Efficacy for Managing Medication and Treatment (26 questions) – (study visit 1 only).
 - The Transplant Satisfaction Questionnaire for Medication – question 14.

Clinical Study Protocol [#SIMPLE]

Table of Contents

SYNOPSIS.....	3
PROTOCOL	9

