13. TREATMENT COMPLIANCE

All subjects in the study will be adequately informed on the specific tacrolimus formulations the patients will receive throughout the study and the importance of compliance to the study protocol.

Clinical Study Protocol [#SIMPLE]

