Demographics	X		
Medical History	X		
Adverse Event Assessment		X	X
Physical exam including vital signs and weight	X	X	X
Safety labs ¹	X	X	X
Tacolimus trough levels		X	X
Data collection from medical records pertaining to infection, immunosuppression, and graft function	X	X	X
Patient Reported Outcome Assessments			
PROMIS – Self-Efficacy for Managing Medications and Treatments v1.0 (26 items)	X		
PROMIS-29 Profile 2.1 (29 items)	X	X	X
Calcineurin Inhibitor Related Symptoms (CIRS) - (5 PRO-CTCAE items)	X	X	X
Transplant Specific(14 PRO-CTCAE items)	X	X	X
Patient Satisfaction: Treatment Satisfaction Questionnaire for Medication-Question 14 (1 question)			X
FACT-G (GP5)	X	X	X

1 Safety Labs (CBC with differential, Electrolytes including creatinine and eGFR)

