15. DATA COLLECTION

Data will be collected at each of the MTAK sites and entered into REDCap. REDCap is a secure web application for building and managing online surveys and databases. REDcap is secure and will be managed by Mayo Clinic Rochester. REDcap is 21 CFR Part 11, FISMA, and HIPPA compliant and hosted on Mayo Clinic's secure servers.

Demographic information: Sex, race/ethnicity, transplant characteristics, and age will be collected.

Medical History: Data to be collected will include medical history and medications, pathologic and laboratory data that are in the pre and post-transplant record.

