16. CRITERIA FOR EVALUATION

Safety

- AEs and SAEs will be assigned by Common Terminology Criteria for Adverse Events (CTCAE) terms and tabulated as incidence rates per tacrolimus formulation.
- Hematology parameters, blood chemistries, and urine results will be monitored regularly as part of the participating centers' standard of care.
- Vital signs, physical condition, and body weight measurements will be monitored regularly.
- Clinically significant infections (confirmed by culture, biopsy, genomic, or serologic findings) that requires hospitalization or active anti-microbial treatment will be tabulated as incidence rates per tacrolimus formulation.
- Cytomegalovirus (CMV), BK Virus, and Epstein-Barr disease will be tabulated as incidence rates per tacrolimus formulation.

Patient Reported Measures and Outcomes

- Patients will complete surveys on their own unless they are unable to. Surveys will be administered on tablets so that data will be recorded in the study's database immediately and securely. The following patient reported outcomes measures will be assessed:
 - HRQoL: PROMIS -29 profile (29 questions) measuring depression, anxiety, fatigue, pain interference, sleep disturbance, physical function, participation in social roles, and pain intensity
 - Symptoms: Calcineurin-inhibitor related symptoms (5 items) and the Transplant related symptoms (14 items) – items from PRO-CTCAE or in PRO-CTCAE format.
 - Symptoms/Tolerability: FACT- G (GP5) – Single item bothersome assessment (1 question).
- Adherence/Medication Satisfaction Measures: The following adherence tools/measures will be assessed at each study visit throughout the study for those patients capable of using an adherence measurement via a digital capture system:
 - The PROMIS Self-Efficacy for Managing Medication and Treatment (26 questions) – (study visit 1 only).
 - The Transplant Satisfaction Questionnaire for Medication – question 14.

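### Adherence power is cited for 220 patients when 204 completers are expected (about 88%); the dnDSA adherence window and the collection of dose records are also not settled

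*Combined protocol and SAP*

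**What the plan says.** Section 3 (secondary endpoint 7; endpoint 9 in the synopsis) compares mean taking adherence, "defined as the percent of prescribed doses taken each day (as measured by electronic monitoring"). The dnDSA endpoint (9 in Section 3, 11 in the synopsis) relates presence of dnDSA to taking and timing adherence cut at 70, 80, 90 and 100%. The synopsis takes adherence between months 4 and 12; Section 3 takes it over the 12 months.

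Section 17 enrols 240, allows 15% dropout and arrives at 204 patients with complete data. It then says that the sample size also serves the adherence comparison, on the basis of 110 per group, means of 75% and 90%, SDs of 38% and 30%, and 90% power from a two-sample t test at two-sided 0.05.

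On collection, Section 16 says that adherence and satisfaction tools "will be assessed at each study visit throughout the study for those patients capable of using an adherence measurement via a digital capture system"; the synopsis has the same sentence. Two tools follow. One is "The PROMIS Self-Efficacy for Managing Medication and Treatment (26 questions) – (study visit 1 only"). The other is satisfaction question 14, which the schedule of events lists as "Patient Satisfaction: Treatment Satisfaction Questionnaire for Medication-Question 14 (1 question") and marks at 12 months only.

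**The concern.** Three things do not fit together.

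- The power statement rests on 220 patients. That is neither the 204 expected with complete data nor the 240 enrolled, so a reader takes away 90% for a sample that the same paragraph does not expect to have.
- The two dnDSA windows define different exposure variables, and the endpoint is built on thresholds.
- Taking and timing adherence need time-stamped dose records, yet the operational sections do not say where these come from, in whom, or when.

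Adherence is in the study title. At stake are 2 of the 10 secondary endpoints in Section 3 (2 of 12 in the synopsis) and the aim in Section 2 of correlating adherence with patient-reported outcomes, satisfaction and quality of life. The primary endpoint is not affected.

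**Working it through.** **Power.** Inputs from Section 17: difference 90 − 75 = 15 points; SDs 38 (twice-daily) and 30 (Envarsus XR); two-sided 0.05; 240 enrolled; 15% dropout. Equal groups are an assumption: 110 per group implies them, but Section 8 says that treatment is not assigned.

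Formula: SE = √(38²/n₁ + 30²/n₂); power ≈ Φ(15/SE − 1.96). The noncentral t figure follows each result.

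1. The plan's figure, 110 per group: SE = √(2344/110) = 4.616; 15/4.616 = 3.249; Φ(1.289) = 90.1% (noncentral t 89.9%). The stated 90% is reproduced.
2. Expected completers: 240 × 0.85 = 204, or 102 per group. SE = √(2344/102) = 4.794; 15/4.794 = 3.129; Φ(1.169) = 87.9% (noncentral t 87.6%).
3. Any split of 204: the smallest possible SE is (38 + 30)/√204 = 4.761, so power is at most Φ(15/4.761 − 1.96) = Φ(1.191) = 88.3% (88.0% with the t distribution). No split reaches 90%. The pooled-variance t test does not exceed about 88% either.
4. Unequal groups, as an assumption because the documents give no split (normal approximation, 204 in total): 60:40 gives 85.0% to 88.1%, and 70:30 gives 78.3% to 85.3%, depending on which group is smaller.
5. What 220 contributors would require: 1 − 220/240 = 8.3% loss, against the 15% planned. Put differently, 240 − 204 = 36 dropouts are expected, and 220 − 204 = 16 of them (44%) would need usable partial records, with all 204 completers also contributing and the groups near equal.

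**Window.** Take a hypothetical patient with 70% adherence in months 0 to 4 and 95% in months 4 to 12. The synopsis window gives 95%, above the 90% cut. The Section 3 window gives (4 × 70 + 8 × 95)/12 = 86.7%, below it. The same patient changes category.

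**Collection.** The places where dose records could appear are:

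- Visit lists (Section 14): consent, history, examination, laboratory tests, trough level and surveys.
- Schedule of events: no adherence row. The nearest row is "Data collection from medical records pertaining to infection, immunosuppression, and graft function".
- Section 15: demographics, and "Data to be collected will include medical history and medications, pathologic and laboratory data that are in the pre and post-transplant record".
- Section 13: patients are "adequately informed on the specific tacrolimus formulations the patients will receive throughout the study and the importance of compliance to the study protocol"; nothing is measured.
- Section 11: drug comes from the patient's own pharmacy; no device or monitored packaging is mentioned.
- Section 16 and the synopsis (Study Method): a digital capture system is named, but the only tools listed are the two questionnaires. One belongs to visit 1 and the other to visit 3, so neither is done at visit 2 and neither fits the statement that tools are used at every visit.
- Section 9: lists both questionnaires among measures taken at both study visits. This conflicts with Section 14, which has three visits and gives each questionnaire once.

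**The case against.** The strongest reply on power is that the claim is conditional and correct: 110 per group does give 90%. A reader might infer an arithmetic error; there is none. Nor is 88% the only possible value. The 204 are patients with complete data at the study endpoint, in a sentence about patient-reported items. Adherence accrues daily, and nothing in the plan confines it to month-12 completers. If all 240 contributed in equal groups, power would be 92.2%. All of this stands. What remains is that the plan ties its adequacy claim to a number that it never derives and does not say who contributes. The shortfall is small for a secondary endpoint in a pilot study.

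On collection, a reader might infer that no doses are recorded at all. The documents do not support that. Section 3 and the synopsis name electronic monitoring, Section 16 and the synopsis name digital capture, and continuous monitoring need not be a clinic-visit procedure. The supportable statement is that the operational description is incomplete.

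A reader might also want a power figure for measurement limited to patients "for those patients capable of using an adherence measurement via a digital capture system". The restriction would lower power, but the documents give no share, so the amount cannot be computed. Likewise, Section 17 says that adherence will be analysed with models similar to the baseline-adjusted ones. That leaves the covariates open and does not show that a baseline-adherence term is intended.

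**Conclusion.** The point holds in three limited parts. First, the adherence power is cited for a sample that does not match the expected completers: about 88% rather than 90% if only the 204 contribute in equal groups, a loss of 87.6% against 89.9%, or 2.3 points. This assumes the plan's means and SDs and dose records from every completer; marked imbalance or restricted monitoring would lower it further. Second, the synopsis and Section 3 give different adherence windows for the dnDSA endpoint. This is a plain conflict that can reclassify patients. Third, the source, population and timing of dose records are not specified, and Sections 9, 14 and 16 and the synopsis disagree on when the two questionnaires are given. The second and third parts bear more on interpretation than the 2-point power difference does.

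**What to change.** - Section 17: restate adherence power as about 88% at 204 completers in equal groups, or state that 220 patients must contribute adherence data (at most 8.3% loss from 240).
- Synopsis endpoint 11 and Section 3 endpoint 9: use one adherence window.
- Schedule of events and Section 15: add the dose-record source, which patients are monitored, and when records are collected.
- Synopsis (Study Method), Section 9 and Section 16: reconcile the questionnaire timings with the visit lists and schedule in Section 14.
- If electronic monitoring is not in use: state that the taking-adherence endpoint, the adherence–dnDSA endpoint and the adherence power claim cannot be supported.

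The cost is a slightly lower stated power and an amendment, which needs IRB approval before it is implemented (Sections 20 and 21). If monitoring is not in use, two secondary endpoints are lost. Timing matters: version 3.0 is dated 8 April 2021 and the estimated last completion is May 2021. The documents do not give the actual study status, but dose records not already captured cannot be recovered.

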4. PATIENT POPULATION

General Consideration:

The study population is composed of de novo solitary kidney transplant recipients who meet inclusion and exclusion criteria and have not been subject to investigational treatments.

Enrollment Rationale: The Multicenter Transplant Alliance Kidney Consortium collectively transplants more than 1,500 people each year (10% of the total number of kidney transplants in the United States annually). Approximately 60% of these patients will be eligible for this study. We consider a 12 month enrollment time to be a conservative estimate.

Clinical Study Protocol [#SIMPLE]

Screening Failure: Subjects who do not meet the eligibility criteria as outlined below during the screening phase of the study will be considered screening failures.

Inclusion criteria:

Each patient must meet all of the following inclusion criteria to be enrolled in the study:

- Patient is an adult (18 years of age or older).
- Treatment with Envarsus XR® or immediate-release, twice-daily tacrolimus has been indicated by patient's transplant care team.
- Patient is a recipient of a deceased or living donor kidney transplant.
- Patient is able to comply with study procedures for the entire length of the study.
- Patient has been informed about the study survey and has signed an informed consent form.

Exclusion criteria:

Patients meeting any of the following exclusion criteria are not to be enrolled in the study:

- Patient is unable or unwilling to complete study patient reported outcome questionnaires.
- Patient is currently receiving azathioprine
- Patient is currently receiving an mTOR inhibitor (sirolimus, everolimus)
- Patient is currently receiving an belatacept
- Patient has received investigational immunosuppression 1 month prior to transplant or post-transplant
- Patient is in a setting where a professional care taker is responsible for dispensing subject's medication.

